### **6.3.3 Anticipated risks and safety concerns of everolimus**

It is anticipated that the patients entering the roll-over protocol have tolerated everolimus treatment and are anticipated to benefit from continued treatment.

Guidelines and recommendations for the management of specific everolimus study drug induced toxicities (hyperglycemia, hyperlipidemia, stomatitis, infectious pneumonitis, reactivation of Hepatitis B and C) are provided in the parent protocol and the current everolimus IB.

## **6.4 Concomitant medications**

### **6.4.1 Permitted concomitant therapy**

In general, concomitant medications/therapies deemed necessary for the supportive care of the patient is permitted.

### **6.4.2 Permitted concomitant therapy requiring caution and/or action**

Everolimus is metabolized by CYP3A4 in the liver and to some extent in the intestinal wall. Therefore, the following are recommended:

- Co-administration with strong inhibitors of CYP3A4 (e.g., ketoconazole, itraconazole, ritonavir) or P-glycoprotein (PgP) inhibitor should be avoided.
- Co-administration with moderate CYP3A4 inhibitors (e.g., erythromycin, fluconazole) or PgP inhibitors should be used with caution. If a patient requires co-administration of moderate CYP3A4 inhibitors or PgP inhibitors, reduce the dose of study drug to half the currently used dose. Additional dose reductions to every other day may be required to manage toxicities. If the inhibitor is discontinued, the study drug dose should be returned to the dose used prior to initiation of the moderate CYP3A4/PgP inhibitor.
- Seville orange, star fruit, grapefruit and their juices affect P450 and PgP activity. Concomitant use should be avoided.
- Co-administration with strong inducers of CYP3A4 should be avoided. If a patient requires co-administration of strong CYP3A4 inducers (i.e., phenytoin, carbamazepine, rifampin, rifabutin, phenobarbital, St. John's wort), an increase in the dose of study drug up to twice the currently used daily dose should be considered, 5mg increments. Enzyme induction usually occurs within 7-10 days; therefore study drug dose should be increased by one increment 7 days after the start of the inducer therapy. If no safety concerns are seen within the next 7 days, the dose can be increased again one additional increment up to a maximum of twice the daily dose used prior to initiation of the strong CYP3A4 inducer.
- This dose adjustment of study drug is intended to achieve similar AUC to the range observed without inducers. However, there are no clinical data with this dose adjustment in patients receiving strong CYP3A4 inducers. If the strong inducer is discontinued the study drug dose should be returned to the dose used prior to initiation of the strong CYP3A4/PgP inducer.

Please refer to [Table 6-2](#) listing relevant inducers and inhibitors of CYP3A and to [Table 6-3](#) for a list of relevant substrates, inducers, and inhibitors of PgP. Please refer to the most recent Investigator's Brochure for a complete list.

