### **Pharmacokinetics**

Everolimus is rapidly absorbed after oral administration, with a time to reach the maximum drug blood concentration ( $t_{max}$ ) of 1-2 hours postdose. The extent of absorption is estimated at above 11%. The area under the blood concentration-time curve (AUC) is dose-proportional over the dose range of 5 to 70 mg tested while maximum drug blood concentration ( $C_{max}$ ) appears to plateau at dose levels higher than 20 mg. The terminal half-life in cancer patients averaged 30 hours, which is similar to that in healthy subjects. A high-fat meal altered the absorption of everolimus with 1.3 hour delay in  $t_{max}$ , a 60% reduction in  $C_{max}$  and a 16% reduction in AUC. In whole blood, approximately 80% of everolimus is contained in red blood cells. Of the fraction of drug contained in plasma, 74% is protein-bound. The apparent distribution volume ( $V_z/F$ ) after a single dose was 4.7 L/kg. Everolimus is eliminated by metabolism, mainly by hydroxylation, then excreted into the feces >80%.

Everolimus is mainly metabolized by CYP3A4 in the liver and to some extent in the intestinal wall. Everolimus is also a substrate of P-glycoprotein (PgP). Therefore, absorption and subsequent elimination of systematically absorbed everolimus may be influenced by medicinal products that interact with CYP3A4 and/or P-glycoprotein. In vitro studies showed that everolimus is a competitive inhibitor of CYP3A4 and of CYP2D6 substrates, potentially increasing the concentrations of medicinal products eliminated by these enzymes. In two phase III clinical trials in patients following kidney transplantation, strong inhibitors of CYP3A4 (azoles, antifungals, cyclosporine, erythromycin) have been shown to reduce the clearance of everolimus therapy thereby increasing everolimus blood levels. Similarly, Rifampin, a strong inducer of CYP3A4, increases the clearance of everolimus thereby reducing everolimus blood levels. Another drug-drug interaction study of everolimus administered with a sensitive CYP3A4 substrate midazolam showed that while everolimus did not influence the hepatic

metabolism of midazolam, it led to minor increases in bioavailability of midazolam likely due to influences of pre-systemic metabolism. Caution should be exercised when co-administering everolimus with CYP3A4 inhibitors, inducers, or substrates with a narrow therapeutic index.

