**Table 6-2 Clinically relevant drug interactions: inducers, and inhibitors of isoenzyme CYP3A**

Inducers
Strong inducers: avasimibe, carbamazepine, mitotane, phenobarbital, phenytoin, rifabutin, rifampin (rifampicin), St. John's wort (hypericum perforatum)
Moderate inducers: bosentan, efavirenz, etravirine, genistein, modafinil, naftillin, ritonavir, [talviraline], thioridazine, tipranavir
Weak inducers: amprenavir, aprepitant, armodafinil (R-modafinil), bexarotene, clobazam, danshen, dexamethasone, Echinacea, garlic (allium sativum), gingko (ginkgo biloba), glycyrrhizin, methylprednisolone, nevirapine, oxcarbazepine, pioglitazone, prednisone, [pleconaril], primidone, raltegravir, rufinamide, sorafenib, telaprevir, terbinafine, topiramate, [troglitazone] , vinblastine
Inhibitors
Strong inhibitors: boceprevir , clarithromycin, cobicistat, conivaptan, elvitegravir, indinavir, itraconazole, ketoconazole, lopinavir, mibefradil, nefazodone, neflifavir, posaconazole ( Krishna et al 2009 ), ritonavir, saquinavir, telaprevir , telithromycin, tipranavir, troleandomycin, voriconazole
Moderate inhibitors: Amprenavir, aprepitant, atazanavir, casopitant, cimetidine, ciprofloxacin, cyclosporine, darunavir, diltiazem, dronedarone, erythromycin, fluconazole, fosamprenavir, grapefruit juice (citrus parasida fruit juice), imatinib, schisandra sphenanthera, tofisopam, verapamil

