**Table 6-3 Clinically relevant drug interactions: substrates, inducers, inhibitors of PgP and PgP/CYP3A dual inhibitors**

Substrates
digoxin, fexofenadine, indinavir, vincristine, colchicine, topotecan, paclitaxel, talinolol, everolimus
Inducers
rifampin, St John's wort
PgP Inhibitors and PgP/CYP3A Dual Inhibitors

amiodarone, azithromycin, captopril, carvedilol, clarithromycin, conivaptan, diltiazem, dronedarone, elacridar, erythromycin, felodipine, fexofenadine, fluvoxamine, gingko (ginkgo biloba), indinavir, itraconazole, lopinavir, mibefradil, milk thistle (silybum marianum), neflifavir, nifedipine, nitrendipine, paroxetine, quercetin, quinidine, ranolazine, rifampin, ritonavir, saquinavir, Schisandra chinensis, St John's wort (hypericum perforatum), talinolol, Telaprevir, telmisartan, ticagrelor, tipranavir, tolvaptan, valspar, verapamil

Reference: Internal Clinical Pharmacology Drug-drug interaction (DDI) memo, updated 29-Oct-2012 which summarizes DDI data from three sources including the FDA's "Guidance for Industry, Drug Interaction Studies", the University of Washington's Drug Interaction Database, and Indiana University School of Medicine's Drug Interaction Table.

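### Protocol Section 6.4.2 places PgP inhibitors under both an avoid and a caution recommendation, and for 24 of the 39 listed agents the protocol has no tie-breaker

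*Protocol*

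**What the plan says.** Protocol Section 6.4.2 gives recommendations on drugs that alter everolimus metabolism or transport.

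- First bullet: "Co-administration with strong inhibitors of CYP3A4 (e.g., ketoconazole, itraconazole, ritonavir) or P-glycoprotein (PgP) inhibitor should be avoided".
- Second bullet, default: "Co-administration with moderate CYP3A4 inhibitors (e.g., erythromycin, fluconazole) or PgP inhibitors should be used with caution".
- Second bullet, conditional step: "If a patient requires co-administration of moderate CYP3A4 inhibitors or PgP inhibitors, reduce the dose of study drug to half the currently used dose". When the inhibitor stops, everolimus is "returned to the dose used prior to initiation of the moderate CYP3A4/PgP inhibitor".

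The section then sends the reader to Table 6-2 for CYP3A agents, to Table 6-3 for PgP agents, and to the Investigator's Brochure for a complete list. Table 6-2 divides CYP3A inhibitors into strong and moderate. Table 6-3 has a single row, headed "PgP Inhibitors and PgP/CYP3A Dual Inhibitors", with no grading.

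On CYP3A strength, the Pharmacokinetics text in Section 1.2.1.2 says that "strong inhibitors of CYP3A4 (azoles, antifungals, cyclosporine, erythromycin) have been shown to reduce the clearance of everolimus therapy". The moderate list in Table 6-2 includes "cyclosporine, darunavir, diltiazem, dronedarone, erythromycin, fluconazole".

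**The concern.** The same ungraded class, PgP inhibitors, appears in two adjacent bullets with different defaults: avoid in one, caution in the other. A site that starts from the first bullet may withhold the comedication. A site that starts from the second may give it and, if the patient requires it, halve everolimus. Both would be following the text.

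This matters mainly for consistent and safe handling of an interaction, in a study whose only objective is long-term safety. Section 12 allows no authorised deviations, so sites need one instruction that they can apply. The inconsistency would also be hard to see afterwards. Pharmacokinetics are not assessed (Section 7.2.3). Protocol Section 10.3 and SAP Section 1.1.4 both have concomitant therapies in their titles, but they plan only everolimus dose and exposure outputs.

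The differing strength labels for a few CYP3A4 inhibitors are a secondary matter. In Section 6.4.2 the strong or moderate label decides which bullet applies to a CYP3A4 inhibitor.

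**Working it through.** The plan states no figure to reproduce. The check compares texts and counts agents.

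**Step 1. The two bullets side by side**

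| | First bullet | Second bullet |
|---|---|---|
| CYP3A4 inhibitors covered | strong | moderate |
| PgP inhibitors covered | no grade stated | no grade stated |
| Default | avoid | caution |
| If the patient requires the drug | nothing stated | halve everolimus |

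The CYP3A4 inhibitors are divided between the bullets by grade. The PgP inhibitors are not divided.

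**Step 2. Can the tables divide them?** Inputs are the inhibitor row of Table 6-3 and the strong and moderate inhibitor lists of Table 6-2, matched by exact name. Table 6-2 contains a different Schisandra species from Table 6-3, and I did not count it as a match.

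- Distinct agents in the Table 6-3 inhibitor row: 39. The whole table has 9 substrate + 2 inducer + 39 inhibitor = 50 entries, or 45 distinct agents, so 39 describes that row only.
- Also strong in Table 6-2: 11. These are itraconazole and ritonavir (both named in the first bullet), saquinavir, clarithromycin, tipranavir, conivaptan, telaprevir, indinavir, neflifavir, lopinavir and mibefradil.
- Also moderate in Table 6-2: 4. These are erythromycin (named in the second bullet), verapamil, diltiazem and dronedarone.
- In neither inhibitor list: 39 − 11 − 4 = 24. Examples are amiodarone, carvedilol, nifedipine, paroxetine and telmisartan.
- Of those 24, rifampin and St John's wort are also strong inducers in Table 6-2, which is a separate question. Without them: 24 − 2 = 22.

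The number of agents without a resolved instruction is therefore 24 if the CYP3A grade may decide (22 without the two inducers), and 39 on a strictly literal reading. The protocol does not say that the CYP3A grade decides.

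**Step 3. Strength labels**

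| Agent | Section 1.2.1.2, Pharmacokinetics | Section 6.4.2 | Table 6-2 |
|---|---|---|---|
| Erythromycin | strong | moderate | moderate |
| Cyclosporine | strong | not named | moderate |
| Fluconazole | strong, as an azole | moderate | moderate |
| Ketoconazole, itraconazole | strong, as azoles | strong | strong |
| Posaconazole, voriconazole | strong, as azoles | not named | strong |

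The mismatch covers three agents: erythromycin, cyclosporine and fluconazole.

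**The case against.** The best defence is that the bullets can be read together. The inducer bullet in the same section uses an avoid-then-adjust pattern: "Co-administration with strong inducers of CYP3A4 should be avoided. If a patient requires co-administration of strong CYP3A4 inducers". Read that way, the first inhibitor bullet gives the preference and the second says what to do when the drug is needed. The closing phrase of the second bullet, which joins CYP3A4 and PgP after the word moderate, also hints that the strong and moderate split was meant for both classes. The Investigator's Brochure may settle the rest.

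Part of this stands. Halving is conditional on need, so the section does not simply tell sites to give PgP inhibitors at half dose. Nor does the first bullet prohibit anything: these are recommendations in a section on permitted therapy, and Section 6.4.3 on prohibited therapy names only systemic anticancer agents.

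The rest does not remove the problem.

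- The inducer pattern sits in one bullet for one class. The second inhibitor bullet has its own default, caution, which differs from avoid. Applied to every agent in the Table 6-3 row, the sequence would also bring itraconazole and ritonavir, named in the first bullet, under the halving step.
- A PgP strength split cannot be applied from Table 6-3, which has no grades. The joined wording is weak evidence, because the inducer text ends with a similar CYP3A4/PgP phrase although its rule names only CYP3A4.
- The brochure is cited here for a complete list, not as overriding either bullet. Its content is not available to this review, so the finding is limited to what the protocol itself resolves.

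On the labels, the Pharmacokinetics text is background about kidney-transplant trials. It advises caution and gives no instruction to avoid, so its mismatch with Table 6-2 does not create a second conflicting instruction.

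**Conclusion.** The inconsistency is real and should be fixed. One ungraded class has two defaults in adjacent bullets. For 24 of the 39 agents in the Table 6-3 inhibitor row (22 without rifampin and St John's wort), nothing in the protocol shows which default applies. The count of 24 assumes that the CYP3A grade in Table 6-2 may sort the other 15, a rule the protocol leaves unstated. The label mismatch for erythromycin, cyclosporine and fluconazole is secondary.

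A reader might infer three stronger things that the documents do not support.

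- **That all 39 agents carry incompatible instructions.** This needs a strictly literal reading that ignores both the Table 6-2 grades and the condition on halving.
- **That sites would differ two-fold in everolimus exposure.** Halving a dose is a two-fold difference in dose only. The Pharmacokinetics section says that CYP3A4 inhibitors reduce clearance and raise blood levels, so the net difference could be small or go either way. The documents give no figure.
- **That adverse event frequency is biased.** The analysis is descriptive and has no comparator. Dose is already at the investigator's discretion (Sections 6.1.1 and 6.3.1). Dose changes are recorded on the eCRF (Section 6.6), and everolimus dosing is listed by patient (Protocol Section 10.3, SAP Section 1.1.4). Different handling between sites is possible but not shown.

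The point has no bearing on sample size or error rates.

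**What to change.** The sponsor should reconcile the two inhibitor bullets of Section 6.4.2 so that each PgP inhibitor falls under one instruction. If two classes of PgP inhibitor are intended, mark the class of each agent in Table 6-3 and state which bullet governs agents that appear in both tables. Align the strong or moderate label of erythromycin, cyclosporine and fluconazole across the Pharmacokinetics text of Section 1.2.1.2, Section 6.4.2 and Table 6-2. Which instruction and which label apply is a clinical decision for the sponsor, and this review takes no position on it.

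The cost is amendment wording and, at most, one added column in Table 6-3. No procedures, patients or analyses are added.

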#### 6.1.1 Dosing regimen

**Table 6-1 Dose and treatment schedule**

Investigational treatments	Pharmaceutical form and route of administration	Dose	Frequency and/or Regimen
RAD001/everolimus	Tablet for oral use	2.5 – 10 mg/day	Daily

Everolimus will be provided as 2.5 mg or 5 mg tablets. The investigational treatment is to be stored in a secure locked area while under the responsibility of the investigator. The investigator should assess compliance of study drug at each patient visit (see [Section 6.6.3.1](#)). Receipt and dispensing of investigational drug must be recorded by an authorized person at the investigator's site (see [Section 6.6.3.2](#)).

At the time of transition to the roll-over study, the starting dose of everolimus should be the same as the last dose that was given in the parent study. Dose modification thereafter may be done at the discretion of the investigator based upon what is in the patient's best interest.

Patients will be instructed to take everolimus orally with a glass of water, once daily at the same time each day, either consistently with food or consistently without food. Dietary habits at the time of enrolling in the study from the parent study should be kept as consistent as possible throughout the study. The tablet should be swallowed as a whole and should not be chewed or crushed.

Please refer to the current everolimus IB and [Section 6.3](#) for further important information on potential dosing precautions regarding concomitant medication interaction with cytochrome p450, p-glycoprotein, and CYP3A4 and the recommended dosing guidance.

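### At 2.5 mg/day, a permitted dose, the 5 mg step in the strong-inducer rule of Protocol 6.4.2 overshoots the rule's own twice-dose maximum, and no smaller step is given

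*Protocol*

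**What the plan says.** Section 6.4.2 of the protocol first advises against the combination: "Co-administration with strong inducers of CYP3A4 should be avoided". For a patient who nevertheless needs such a drug, it says that "an increase in the dose of study drug up to twice the currently used daily dose should be considered, 5mg increments". The timing follows. The "study drug dose should be increased by one increment 7 days after the start of the inducer therapy", and if the next 7 days raise no safety concern, "the dose can be increased again one additional increment up to a maximum of twice the daily dose used prior to initiation" of the inducer. The purpose is given as well: "This dose adjustment of study drug is intended to achieve similar AUC to the range observed without inducers".

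Three other places bear on this.

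- Section 6.1.1 with Table 6-1 sets the dose range at 2.5 to 10 mg/day and adds: "Everolimus will be provided as 2.5 mg or 5 mg tablets". Patients enter on their last parent-study dose, and "Dose modification thereafter may be done at the discretion of the investigator". The section also sends the reader to the investigator's brochure and to Section 6.3 "for further important information on potential dosing precautions regarding concomitant medication interaction with cytochrome p450, p-glycoprotein, and CYP3A4 and the recommended dosing guidance".
- Section 6.3.1 lets the parent protocol's dose modifications apply if the investigator so decides, and limits everolimus to 10 mg/day.
- The SAP lists everolimus doses by patient and summarises exposure. It contains no dosing rule.

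**The concern.** The inducer rule has one step size (5 mg) and one maximum (twice the dose before the inducer). A fixed step combined with a proportional maximum must fail at a low enough starting dose, so the question is whether that happens inside the permitted range. It does, at the bottom of it: a patient on 2.5 mg/day has only 2.5 mg of room, half of one increment.

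The sentence that orders the first increment mentions no maximum. The maximum appears in the sentence before it and again with the second increment. An investigator working through the steps for a patient on 2.5 mg/day meets two instructions that cannot both be followed, and no statement of which yields. If the maximum wins, the listed step gives no adjustment at all, and the aim of keeping exposure similar to that without the inducer cannot be pursued by the rule as written. What is at stake is a clear dosing instruction in a safety study, not the analysis.

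**Working it through.** The plan gives no worked example for this rule, so there is no figure to reproduce first. The check is direct arithmetic.

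**Inputs**
- Permitted daily dose: 2.5 to 10 mg (Table 6-1).
- Tablets: 2.5 mg and 5 mg (Section 6.1.1). The daily doses checked are therefore d = 2.5, 5, 7.5 and 10 mg.
- Step: 5 mg (Section 6.4.2).
- Maximum under the rule: 2d (Section 6.4.2).
- General limit: 10 mg/day (Section 6.3.1).

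**Formulas**
- Dose after the first step = d + 5; after the second = d + 10.
- Room under the maximum = 2d − d = d, so the number of full 5 mg steps that fit is d/5 rounded down.
- The first step is allowed only if d + 5 ≤ 2d, that is, if d ≥ 5 mg.

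| Dose before inducer, d (mg) | Maximum 2d (mg) | After first step (mg) | Within 2d? | After second step (mg) | Within 2d? | Full steps under 2d | First step within 10 mg/day? |
|---|---|---|---|---|---|---|---|
| 2.5 | 5 | 7.5 | no | 12.5 | no | 0 | yes |
| 5 | 10 | 10 | yes | 15 | no | 1 | yes |
| 7.5 | 15 | 12.5 | yes | 17.5 | no | 1 | no |
| 10 | 20 | 15 | yes | 20 | yes | 2 | no |

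**At 2.5 mg/day.** The first step gives 2.5 + 5 = 7.5 mg. That is 7.5/2.5 = 3.0 times the prior dose and 7.5 − 5 = 2.5 mg above the maximum, or 2.5/5 = 50% over. A 2.5 mg step instead gives 2.5 + 2.5 = 5 mg, which is 5/2.5 = 2.0 times the prior dose and exactly at the maximum. A second 2.5 mg step would give 7.5 mg and break it, so one small step completes the escalation.

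**Against the 10 mg/day limit, if it applies during inducer use.** From 7.5 mg/day the first step reaches 12.5 mg, which is 2.5 mg (25%) over. From 10 mg/day it reaches 15 mg, which is 5 mg (50%) over. From 5 mg/day it reaches 10 mg and meets the limit. Taking both limits together, the first step as written is possible at one of the four doses, 5 mg/day.

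**The case against.** The strongest reply is that the rule already tells the site where to end up. The bullets are introduced as recommendations, an increase is only to be considered, and the maximum is stated twice. For a patient on 2.5 mg/day that points to 5 mg/day, which the supplied tablets can deliver and which the investigator's discretion in Sections 6.1.1 and 6.3.1 would permit. Much of this stands. It means that the gap is a missing step size, not a missing safe dose. It does not close the gap, because the discretion clauses give no increment, and a 2.5 mg step departs from the only one written.

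A reader might infer that the protocol directs sites to triple the dose. The text does not support that. Reaching 7.5 mg requires applying the increment while ignoring the limit in the same sentence.

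A second reply is that the investigator's brochure or the parent protocol may cover this dose. The protocol refers to both and neither is available here, so this cannot be checked. The point is therefore limited to what the protocol itself says; it does not follow that sites have no instruction from any source.

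A third reply is that the emphasis is misplaced, because the 10 mg/day limit affects more doses than the 2.5 mg case does. That is true if the limit applies. It would also be wrong to infer that 2.5 mg/day is the only problem dose, since that holds only if the limit is set aside. Section 6.4.2 does not say which is intended. Section 6.1.1 sends readers to Section 6.3 on interactions, which leans towards the limit applying but does not settle it.

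**Conclusion.** The point holds as an internal conflict in a dosing recommendation at one permitted dose. At 2.5 mg/day the stated increment exceeds the rule's own maximum by 2.5 mg, no full increment fits, and the protocol gives no smaller one. On the best reading the maximum governs, so the expected consequence is no increase or an ad hoc one.

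The conditional second part is that, if the 10 mg/day limit in Section 6.3.1 also binds during inducer use, first steps from 7.5 and 10 mg/day are ruled out too, leaving 5 mg/day as the only dose of the four at which the rule works as written.

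The conclusion assumes daily doses built from the two supplied tablet strengths. The scope is narrow: strong inducers are to be avoided, and the documents do not show how many patients take 2.5 mg/day together with one. Nothing here supports a claim about the size of any effect on exposure or tolerability, and the planned safety summaries do not change. The correction is worth making because it removes a contradiction from a dosing instruction at very little cost.

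**What to change.** In Section 6.4.2, replace the step-size wording with:

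> Increase in increments of up to 5 mg; no step may take the dose above twice the dose used before the inducer. For a patient on 2.5 mg/day, use one 2.5 mg increment to 5 mg/day and no second increment.

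The general condition should apply to every step and not only to the lowest dose, because second increments from 5 mg/day (15 against 10 mg) and 7.5 mg/day (17.5 against 15 mg) also exceed the maximum. The step from 5 to 10 mg/day stays as it is.

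In the same or the next amendment, make Sections 6.3.1 and 6.4.2 consistent by stating in 6.4.2 whether the 10 mg/day limit also caps the dose during strong-inducer use. If it does, the first steps to 12.5 and 15 mg are excluded. If it does not, 6.4.2 should say that it is an exception.

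The text cost is a few sentences. No new tablet strength, visit or data item is needed, and the SAP is untouched. Section 12.1 requires any change to go through a written amendment with sponsor and ethics committee approval, and health authority approval where required, so it is sensible to add this to an amendment made for other reasons.
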